9.2.3 Study visits

The enrolment period of the study will last for a maximum of 9 months. Enrolled patients will undergo two study visits: visit 1 (baseline visit) during screening and enrolment, and visit 2 (follow up visit) 3 months (± 2 weeks) after the baseline visit. Instead of the regular visit 2 at 3-months, an unscheduled visit will take place in case of premature discontinuation to assess the specific reason for discontinuation, to complete main data collection parameters and to check for compliance and safety issues.

9.2.4 Study discontinuation

Boehringer Ingelheim reserves the right to discontinue the study overall or at a particular study site at any time for the following reasons:

1. Failure to meet expected enrolment goals overall or at a particular study site.
2. Emergence of any efficacy/safety information that could significantly affect continuation of the study, or any other administrative reasons, i.e. lack of recruitment.
3. Violation of the protocol, the contract, or applicable laws and regulations for non-interventional studies, which could disturb the appropriate conduct of the NIS.

The investigator / the study site will be reimbursed for reasonable expenses incurred in case of study termination (except in case of the third reason).

Patients will be automatically discontinued from the study immediately after the treatment of interest in the study has been discontinued.

Additional specific withdrawing reasons for discontinuing a patient from this NIS are: voluntary discontinuation by the patient who is at any time free to withdraw from the study, any situation where the investigator believes that the continuation in the study may be detrimental to the patient's health, and if a patient is included in an interventional clinical trial at any time during his/her participation in this NIS.

9.3 VARIABLES

9.3.1 List of variables

In this NIS, the following data collection about the changes after the switch from a maintenance therapy with tiotropium monotherapy (Spiriva® Handihaler®) to dual therapy with tiotropium bromide plus olodaterol (Spiolto® Respimat®) on quality of life and health status in 1500 COPD patients treated in the Greek private and public sector pulmonary offices and clinics will be collected in an e-CRF.

The data collection both at the baseline visit (immediately after the switch) and at 3 months visit (three months later) will consist of the following list of variables:

- ***COPD history and clinical characteristics at baseline and changes up to 3-months visit:***

Time since COPD diagnosis

COPD severity based on GOLD assessment (B, C, D group), if available

COPD: Chronic bronchitis/Emphysema/Other COPD

Smoking history and current status

Eosinophilia

FEV1/FVC ratio, if available

History of exacerbations in the year before baseline visit and between baseline and 3-months visit

- ***Respiratory comorbidities and allergies at baseline and changes up to 3-months visit:***

Pneumonia

Allergic rhinitis

Bronchiectasis

Lung diseases due to external agents

- **Comorbidities at baseline and changes up to 3-months visit:**

Diabetes mellitus

Osteoporosis

Cardiovascular diseases (including heart failure, atrial fibrillation and other arrhythmias)

Malignancies

Anxiety/depression

Insomnia

Pulmonary artery hypertension

Sleep apnea

Gastroesophageal reflux disease

Hemolytic anemia

Atopy

Sinusitis

Emphysema

- **Current and past COPD therapies** (in the period of one year before enrolment)

- **Relevant concomitant medications at baseline and changes up to 3-months visit:**

Use of concomitant inhalers

Other concomitant medications

- [REDACTED] [REDACTED])

- **COPD Assessment Test (CAT) (9)** (see [ANNEX 3](#))

The CAT is a patient-completed questionnaire assessing globally the impact of COPD (cough, sputum, dysnea, chest tightness) on health status. It is a unidimensional score based on 8 items each of them scaling from 0 to 5.

The measurement properties and responsiveness of the instrument were very similar to those of the more complex and longer St George's Respiratory Questionnaire (SGRQ). Further research has supported these findings and established the CAT as a valuable measure of health status in research ([9,10,19–21](#)). Following extensive translation and linguistic validation, the measurement properties and responsiveness of the CAT have been evaluated in many different countries and found to be similar ([9,10,19–21](#)).

Range of CAT scores from 0–40. Higher scores denote a more severe impact of COPD on a patient's life. The difference between stable and exacerbation patients was five units. No target score represents the best achievable outcome, however, CAT scores <10 corresponding to mild impact on patients life are usually considered those representing patients without impaired health status ([21,22](#)).

- **EQ-5D-5L questionnaire (23,24)** (see [ANNEX 3](#))

The EQ-5D-5L questionnaire is a well-established and commonly used tool for the measurement of a patients QoL. The EQ-5D-5L essentially consists of two parts: the EQ-

5D descriptive system and the EQ visual analogue scale (EQ VAS). The questionnaire was translated and validated for more than 170 languages.

The EQ-5D-5L descriptive system comprises five dimensions (mobility, self-care, usual activities, pain/discomfort and anxiety/depression). Each dimension has three levels (no problems, some problems, and extreme problems) and was self-reported by the patient. The patient's decision results into a 1-digit number that expresses the level selected for that dimension.

The EQ VAS records the patient's self-rated health on a vertical visual analogue scale where the endpoints are labelled 'best imaginable health state' and 'worst imaginable health state'. The VAS can be used as a quantitative measure of health outcome that reflects the patient's own judgement.

- ***Simplified medication adherence questionnaire (SMAQ)*** ([25](#)) (see [ANNEX 3](#))

This tool is a short and simple questionnaire based on questions posed directly to the patient regarding his/her medication-taking habits, which was originally validated for the measurement of adherence in patients on anti-retroviral treatment ([25](#)). The SMAQ has been extensively used for evaluating compliance with treatment for different chronic conditions.

The aim is to assess whether the patient adopts correct attitudes in relation to the treatment for his disease. It is assumed that if the attitudes are incorrect, the patient is not compliant. It has the advantage that it provides information about the causes of non-compliance. The patient is considered as compliant if all questions are answered correctly.

- ***Modified British Medical Research Council (mMRC) Dyspnea Scale*** ([26](#)) ([ANNEX 3](#))

The mMRC Dyspnea Scale quantifies disability attributable to breathlessness, and is useful for characterizing baseline dyspnea in patients with respiratory diseases, especially COPD.

It consists of a five-level rating scale based on the patient's perception of dyspnea in daily activities. For patients with COPD, it is a simple and valid tool to assess disability ([27](#)), and has been reported to be more relevant to patients' health and psychological status than FEV1 ([28](#)).

- ***Patient Satisfaction and Preference*** ([29](#)) (see [ANNEX 3](#))

Patient satisfaction with Respimat® will be measured with the part 1 of the abbreviated Patient Satisfaction Questionnaire (PASAPQ) ([29](#)). The patient preference Spiriva® Handihaler® vs Spiolto® Respimat® will be measured using PASAPQ (part 2).

PASAPQ has been proved as a practical, valid, reliable and responsive instrument for measuring respiratory device satisfaction ([29](#)).

- ***Adverse drug reactions (ADRs), fatal adverse events (AEs) and pregnancies***

9.3.2 Exposures

All included patients will be already receiving LAMA/LABA combination treatment with Spiolto® Respimat® after a recent switch (within one week) from previous maintenance therapy with tiotropium monotherapy (Spiriva® Handihaler®), according to the Greek SmPC. The decision of the treating physician to switch the treatment strategy will be previous and completely independent from the initiation of this NIS. Additionally, the decision will be according to the daily clinical practice in the corresponding center.

The same group of patients at two different time-points (three-months ahead) will be considered for the comparison analyses: within one week after the switch of COPD treatment from tiotropium monotherapy (Spiriva® Handihaler®) to dual therapy with tiotropium bromide plus olodaterol (Spiolto® Respimat®) and three-months after the baseline visit. However, no minimal exposure will be required. Subjects with premature drug discontinuation for any reason will not be excluded from the analysis.

Spiolto® Respimat® contains:

- The long-acting anticholinergic tiotropium bromide. The dose dispensed is 2.5 micrograms of tiotropium per puff, equivalent to 3.124 micrograms tiotropium bromide monohydrate. The dose dispensed is the quantity available to patients after crossing the mouthpiece.
- The selective beta2-adrenoceptor agonist olodaterol. The dose dispensed is 2.5 micrograms of olodaterol per puff (as olodaterol hydrochloride). The dose dispensed is the quantity available to patients after crossing the mouthpiece.

The recommended daily dose of Spiolto® Respimat® for adults is 5 micrograms of tiotropium ion (tiotropium) plus 5 micrograms of olodaterol, equivalent to inhaling 2 puffs from the Respimat® inhaler once daily at the same time of day.

The Summaries of Product Characteristics on Spiolto® Respimat® is contained in the NIS ISF in the “Summary of Product Characteristics” section.

Note: The recommended doses stated in the Summary of Product Characteristics should not be exceeded.

9.3.3 Outcomes

9.3.3.1 Primary outcome

The primary outcome of this NIS will be the mean change in patients' quality of life (QoL) according to the total score of COPD Assessment Test (CAT) within three months after the switch from Spiriva® Handihaler® to Spiolto® Respimat® according to the daily clinical practice.

9.3.3.2 Secondary outcomes

[figure not shown]
The secondary outcomes of the NIS include:

- Change in the proportion of patients with COPD Assessment Test (CAT) ≥ 10 (representing impaired health status) within three months after the switch
- Mean
- change from baseline in the total EQ VAS within three- months after the switch
- Proportion of patients that change (improve/worsen) each of the 5 dimensions of the

EQ-5D-5L within three-months after the switch

- Rate of adherence to medication of COPD patients according to the SMAQ three-months after the switch
- Mean total score in abbreviated PASAPQ (first 13 questions of Part 1) (patient satisfaction with the inhaler device) approximately three-months after the switch.
- Mean score of overall satisfaction according to Question 14 of PASAPQ (Part 1) three-months after the switch.
- Proportion of preference (Spiriva® Handihaler® vs Spiolto® Respimat®) according to PASAPQ (Part 2) three-months after the switch
- Mean score of willingness to continue with inhaler (Spiolto® Respimat®) according to PASAPQ (Part 2) three-months after the switch.

Mean change of patients' dyspnea status according to the mMRC scale within three-months after the switch.

9.4 DATA SOURCES

Patient medical records (paper and/or electronically) and patient reported outcomes from COPD patients as documented by the treating physician in his/her daily practice will be used as data source.

All participating physicians will be obliged to make a note of the patient's participation in the NIS in the patient's medical records.

In the event of possible queries, the participating physician must be able to identify the patient observed. Medical information on the patient must be communicated and analyzed only using the patient number.

During this study, the following has to be completed:

To be completed by the physician:

- [REDACTED]
- Patient medical files (including comorbidities and concomitant medications)
- [REDACTED]

To be completed by the patient at Visit 1 (baseline) and Visit 2 (3-months visit):

- COPD Assessment Test (CAT) (9)
- EQ-5D-5L questionnaire (23,24)
- Modified Medical Research Council (mMRC) questionnaire (26)

To be completed by the patient only at Visit 2 (3-months visit):

- Simplified Medication Adherence Questionnaire (SMAQ) ([25](#))
 - Abbreviated Patient Satisfaction Questionnaire (PASAPQ) ([29](#))

9.5 STUDY SAMPLE SIZE

The sample size determination is not based on a power calculation because no hypotheses will be tested. The primary endpoint of change in score of COPD Assessment Test (CAT) within three months after the switch from Spiriva® Handihaler® to Spiolto® Respimat® will be analysed descriptively by mean and 95% confidence interval. From other studies a mean difference in CAT score of 1.0 and standard deviation of 9.0 are expected.

With a sample size of 1310, a two-sided 95% confidence interval for the difference in paired mean scores will have an interval that extends by no more than 0.5 from the observed difference in means (e.g. an interval from 0.5 to 1.5 for a difference of 1.0), with 90% coverage probability, assuming that the true standard deviation of differences is 9.0 and that the confidence interval is based on the t statistic. The calculation was performed using the MOC3 routine from commercial software nQuery Advisor® 7.0 (██████████ [R15-1331]). To account for a 15% dropout rate, 1507 patients will be needed. Therefore, it was decided to enroll 1500 patients in the study.

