9.7 DATA ANALYSIS

All patients who were included, fulfilled all selection criteria and have received at least one dose of Spiolto® Respimat® will constitute the treated set for the analyses. All analyses will be performed on the treated set. If patients have missing values for an outcome, those patients will be excluded for that outcome's analysis, unless otherwise indicated in [Section 9.7.3](#). For example, if a patient is missing the CAT score at baseline visit and/or at the 3- months visit, that patient will be excluded from the analyses for the primary endpoint of COPD related health status according to CAT and the secondary endpoint of change in CAT after three months of the switch from Spiriva® Handihaler® to Spiolto® Respimat®.

The analyses will relate to the following data:

- COPD history and clinical characteristics
- Reported exacerbations in the year before and during the 3-months study period
- Past COPD therapies (12 months before enrolment)
- COPD related and other relevant concomitant medication
- Respiratory comorbidities and allergies
- Concomitant diseases / Comorbidities
- Respimat® training (Yes/No)
- COPD severity based on GOLD assessment (if available).
- COPD impact on patient's life based on CAT
- Patient's QoL based on EQ-5D-5L
- Adherence to treatment based on SMAQ
- Breathlessness based on mMRC score
- Satisfaction and Preference (abbreviated PASAPQ)
- [REDACTED]
- [REDACTED]
- Adverse Drug Reactions (non-serious & serious), fatal AEs, pregnancies
- Rationale for Spiolto® Respimat® treatment discontinuation (if applicable)
- Details of treatment continuation / discontinuation

[figure not shown]

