9.7.3 Handling of missing data

The extent of missing data will be evaluated and described.

For the primary analysis, no treatment of missing data is planned except the imputation using the last-observation carried forward [LOCF] method if any post-baseline value is available in patients who discontinued before three months and for whom the value will be set as the last available measure.

Any removal from the analysis will be documented, stating the site and patient number as well as the reason for removal.

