### **5. AMENDMENTS AND UPDATES**

#### **5.1 Changes from protocol analysis**

Additional modifications from the CTP made in this SEAP:

- It was stated in CTP to exclude patients with missing values. Missing values will be treated in a different way according to their nature. Missing values due to Intercurrent Event (IE) are taken care at the estimands definitions, on the other hand, missing values not related to IE will be multiple imputed if missingness is greater than 25% for a specific variable.
- It was suggested in the CTP, [REDACTED]  
[REDACTED]
- To assess the potential associations between patient characteristics, treatment, preference [REDACTED]ing

to health status assessed with CAT will not be assessed via univariate methods, however the applicable [REDACTED] are included to the statistical models in the primary and the first secondary endpoint analysis.

[REDACTED]

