#### 11.2.1 Analysis of primary outcome.

11.2.1.1 Mean change in patients' quality of life (QoL) according to the total score of COPD Assessment Test (CAT) within three months after the switch from Spiriva® Handihaler® to Spiolto® Respimat®.

The primary estimand is defined as follows:

- A. Population: Is defined through inclusion/exclusion criteria of the study protocol to reflect the target population.
- B. Variable: Continuous variable response.

- C. Intercurrent Event (IE): Include death, drop-out due to any adverse event (AE) and treatment discontinuation. For patients experiencing an IE, the most extreme unfavourable value will be assigned (CAT score at 3 Months equals to 40).
- D. Population level summary: The change from Baseline of total CAT score within 3 Months.

Mixed model for repeated measurements (MMRM) assuming random missingness will be fitted. The dependent variable will be the CAT score at each visit. Visit, GOLD group, smoking habits, packyears, sex, age, and comorbidities appearing at a rate greater than 5% will be entered as covariates. Patients will be fitted at random and an unstructured covariance matrix will be used, allowing adjustment for correlations between study visits within the study patients. The Kenward- Roger degrees of freedom approximation will be used in the model (ddfm=kr).

Summaries of the estimated mean change from baseline of CAT score at 3 Months will be provided with 95% confidence interval. Model information will be provided as footnote under the corresponding table.

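### Protocol 9.5 adds 15% to 1310 (1507) instead of dividing by 0.85 (1542), so the 1500 to be enrolled cover a loss of at most 12.7%, not 15%

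*Protocol*

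**What the plan says.** Protocol 9.5 makes no power calculation. It justifies the sample size by the width of the confidence interval for the mean CAT change: "With a sample size of 1310, a two-sided 95% confidence interval for the difference in paired mean scores" is to have a half-width of no more than 0.5 with 90% probability. The assumed SD of the differences is 9.0, and "the confidence interval is based on the t statistic". It continues: "To account for a 15% dropout rate, 1507 patients will be needed". It concludes: "Therefore, it was decided to enroll 1500 patients in the study".

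Two further protocol sections decide who counts as evaluable. Under 9.7, if the baseline or three-month CAT score is missing, "that patient will be excluded from the analyses for the primary endpoint", unless 9.7.3 provides otherwise. Section 9.7.3 allows last observation carried forward "if any post-baseline value is available in patients who discontinued before three months".

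The SAP changes the analysis. Section 5.1 says "Missing values will be treated in a different way according to their nature", and section 11.2.1 fits a mixed model for repeated measures (MMRM) in which "The dependent variable will be the CAT score at each visit". The SAP text available gives no new sample-size calculation, and its section 4 refers readers to the protocol for sample-size planning.

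**The concern.** A dropout rate is a fraction of the patients enrolled. To keep n evaluable patients after losing a fraction d, one enrols n/(1 − d). Multiplying by (1 + d) always falls short, and 1507 is what that multiplication gives. Enrolment was then rounded down, which widens the gap.

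The precision target is the only basis offered for the study's size, and the dropout sentence presents 1507 as the number that protects it. If 1507 does not, the stated justification fails at the loss the protocol itself plans for, and a study report that repeats 9.5 would claim a tolerance the design does not have.

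**Working it through.** **Inputs, all from Protocol 9.5:** two-sided 95% t-interval for a paired mean; target half-width 0.5; required probability 90%; SD of differences 9.0; evaluable n 1310; dropout 15%; stated need 1507; planned enrolment 1500.

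**Formulas.** Let s be the sample SD of the changes, with (n − 1)s²/81 distributed as chi-square on n − 1 degrees of freedom, and let t be the 0.975 quantile of Student's t on n − 1 degrees of freedom.

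- Assurance: A(n) = P(t·s/√n ≤ 0.5) = P(χ²₍ₙ₋₁₎ ≤ n(n − 1)·0.5² / (t²·9²)).
- Half-width assured with 90% probability: H(n) = t·9·√(q/(n − 1))/√n, where q is the 0.90 quantile of that chi-square.
- Half-width if s equals 9.0: t·9/√n.

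**Step 1: the base figure reproduces.** A(1309) = 0.8971 and A(1310) = 0.9007, so 1310 is the smallest n that meets the target. Conditioning on the interval covering the true mean gives 1311 instead, which makes no practical difference.

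**Step 2: the dropout step.**

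- 1310 × 1.15 = 1506.5, rounded up to 1507: the protocol's figure.
- 1310/0.85 = 1541.2, rounded up to 1542. Check: 1542 × 0.85 = 1310.7.
- 1507 × 0.85 = 1280.95, so 1507 leaves only 1280 complete patients and fails its own 15%.

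**Step 3: what 1500 supports.** 1500 − 1310 = 190 and 190/1500 = 12.67%. At 15% loss, 1500 × 0.85 = 1275.

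**Step 4: precision at each evaluable n** (paired t-interval, SD 9.0).

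| Evaluable n | Source | A(n) | H(n) | Half-width at s = 9.0 |
|---|---|---|---|---|
| 1310 | target | 0.9007 | 0.5000 | 0.4878 |
| 1280 | 1507 less 15% | 0.7507 | 0.5059 | 0.4935 |
| 1275 | 1500 less 15% | 0.7176 | 0.5070 | 0.4945 |

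**Step 5: how far this carries to the SAP's model.** The MMRM takes the CAT score at each visit as the response, so a patient with only a baseline value still contributes. The 1275 and the 72% therefore do not describe it. As a rough check, a two-visit likelihood estimate was simulated 10,000 times per setting. The assumptions, none of which is in the documents, were normal data, equal SD at both visits, SD of change 9.0, 1500 baseline and 1275 three-month values missing at random, and no covariates. The SAP's assignment of CAT = 40 after an intercurrent event was also left out. The probability of a half-width of at most 0.5 was about 97%, 94%, 92% and 89% at per-visit SDs of 8, 9, 10 and 11. This shows only that baseline-only patients recover much of the lost precision. It does not give the precision of the SAP's primary estimand, because the CAT = 40 rule would change the SD.

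**The case against.** The strongest reply is that 1275 is a worst case. Protocol 9.1 and Table 1 plan an unscheduled visit at premature discontinuation, where feasible, with CAT collected. Section 9.3.2 keeps early discontinuers in the analysis, and 9.7.3 carries their last value forward. At 15% dropout, 0.15 × 1500 = 225 patients drop out. If 35 of them (35/225 = 15.6%) supplied a CAT value, 1310 would be restored. This stands as a limit on the 72% and the 0.507, which hold only if no dropout yields a usable change. It does not rescue 1507: section 9.5 takes no credit for carried-forward values and allows for the full 15%.

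It can also be said that the effect is trivial. The assured half-width grows by 0.007 on a 0–40 scale, and because half-width scales with the SD, a true SD of 9.0 × 0.500/0.507 ≈ 8.88 would cancel it. That is true, and it is why no extra patients are called for. The fall from 90% to 72% looks large because assurance is steep near its threshold.

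Finally, the protocol elsewhere describes the 1500 as approximate, lets recruitment end with the enrolment period, and has been overtaken by the SAP's MMRM. None of this makes 1507 correct. Section 9.5 remains the only sample-size justification, and the SAP points back to the protocol for it.

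**Conclusion.** The concern holds. The base figure of 1310 is right. The dropout inflation uses the wrong operation, and because 1507 matches the multiplication exactly, rounding does not explain it. The correct number is 1542, which is 35 more than 1507 and 42 more than the 1500 to be enrolled. The planned enrolment tolerates a 12.7% loss of usable CAT changes rather than 15%.

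The effect is minor and confined to stated precision. It rests on an SD of change of 9.0, the paired t-interval of 9.5, complete-case exclusion under 9.7, and no CAT value from any dropout. No test, decision rule or clinical conclusion depends on it. It should be corrected because the sentence is wrong as written and the correction costs almost nothing.

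**What to change.** Keep 1500 enrolled. In Protocol 9.5, replace 1507 with 1542 and replace the closing sentence with wording such as:

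*With 1500 enrolled, 1310 evaluable patients are reached if at most 190 (12.7%) lack a usable CAT change. If 15% lack one, 1275 are evaluable and the half-width of the paired 95% t-interval is no more than 0.507 with 90% probability (SD 9.0). These figures refer to the paired t-interval, not to the SAP's MMRM.*

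Counting patients without a usable CAT change, rather than dropouts, keeps the statement correct however many discontinuers supply a value at the unscheduled visit.

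The cost is one number and one sentence. The stated precision at 15% loss becomes 0.507 instead of 0.500. Recruitment, data collection and analysis are unchanged.
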